7.7 Intervention supply and storage

7.7.1 Intervention supplies

Local pharmacies will use the standard preparations from their normal supply chain.

7.7.2 Packaging and labelling

Through the risk-adapted approach, a full risk assessment of the ABBRUPT trial has been conducted including the drug accountability requirements. Drugs will be used within their authorisation, and dispensed according to site's local practices from standard stock. The risk assessment has determined that an additional clinical trial label is not necessary (as covered by Regulation 46 (2) of SI 2004/1031).

7.7.3 Drug storage

The drugs in both arms of the trial will be used as per standard clinical practice, therefore there is no additional requirement, above that of local policy, to monitor temperature during storage. Drugs that have expired or are returned as excess drug should be destroyed in accordance with local practice.

7.7.4 Accountability

Drug accountability will be according to standard operating procedures and local policy guidelines at each participating NHS Trust.

Adherence in both trial arms will be documented on the Follow-Up CRFs using information available in the patient's medical notes.

8 OUTCOME MEASURES

8.1 Pilot Outcomes

- 250 patients recruited from at least 15 sites
- Alternative treatment to randomised arm of <5%
- Drop-out rate of <5%
- ≥90% data completeness of the primary outcome

8.2 Main trial outcomes

Primary outcome

90-day mortality

Secondary outcomes

Clinical Outcomes

- ICU and hospital mortality
- Rates of Cardiovascular events including stroke, myocardial infarction or thromboembolism at 90-days
- Rate of established AF by the end of ICU stay / death/ day 90

Economic Outcomes

- Cost-effectiveness of the interventions
- · Health care resource use including ICU and hospital length of stay

Safety Outcomes

- The number episodes of bradycardia (HR <50 bpm) whilst in hospital and being prescribed the intervention
- Bradycardia and bradycardic arrhythmias with haemodynamic compromise requiring intervention
- Significant hypotension requiring intervention (not including temporarily stopping the trial medication) whilst in ICU
- Heart block
- Arrhythmia with haemodynamic compromise requiring intervention including DC cardioversion

9 TRIAL PROCEDURES

All data will be recorded in the CRFs.

The Visits will be at Baseline (D0), Day 1 (D1), Day 2 (D2), Day 3 (D3), Day 7 (D7), ICU discharge, Hospital Discharge, Day 60 (D60) (+/- 14 days) and Day 90 (D90) (+/- 14 days).

Adverse events should be recorded as soon as the Local Research Team become aware of them. Please see Section 11 **ADVERSE EVENT REPORTING** for further details.

Day 0 (D0)

- Demographics Data:
- Sex, age, height, weight, APACHE score, summary of the relevant medical history, date of admission to hospital and ICU should be recorded at randomisation
- Treatment Allocation:
- Treatment Arm
- Randomisation date and time
- Time and date of first AF will be recorded. The diagnosis of AF should be confirmed by a competent clinician.
- Components in order to calculate the SOFA score
- Clinical Data Data for the 24 hours prior to randomisation should be recorded. This can be collected from the clinical records and may be collected retrospectively.
- Cardiovascular: time and date of onset of AF and HR, Mean Arterial Pressure (MAP), Inotrope and Vaospressor type and dose every 6 hours.
- Biochemistry: Sodium, Potassium, Urea, Creatinine, Magnesium and C-Reactive Protein (CRP).
- *Haematology:* White Cell Count, Lymphocyte, Monocyte, Neutrophil and Platelet count and the haemoglobin.

Day 1 (D1), Day 2 (D2), Day 3 (D3), and Day 7 (D7)

- Clinical Data This can be collected from the clinical record and may be collected retrospectively
- Cardiovascular: time and date of onset of AF and HR, Mean Arterial Pressure (MAP), Inotrope and Vaospressor type and dose every 6 hours.
- Biochemistry: Sodium, Potassium, Urea, Creatinine, Magnesium and C-Reactive Protein (CRP).
- *Haematology:* White Cell Count, Lymphocyte, Monocyte, Neutrophil and Platelet count and the haemoglobin.
- Expected Serious Adverse Events:
- Death related to the underlying cause of ICU admission
- Cardiovascular failure, including the need for vasopressors/ inotropes
- Respiratory failure, including mechanical ventilation and acute lung injury
- Hepatic impairment as measured by Bilirubin rise of >100 μ mol/L or Transaminases >1000 μ L/L
- Acute Kidney Injury, including the need for renal replacement therapy
- Haematological / coagulation failure, including thrombocytopaenia and Disseminated Intravascular Coagulopathy (DIC)
- Delirium / confusion

Discharge From ICU

- Date of discharge from ICU
- Mortality status
- Medication groups listed on CRF Drug Log should be recorded especially those for risk reduction of stroke (such as anti-coagulation with Apixaban or Rivaroxaban or Warfarin or other) and the ongoing treatment with either of the study drugs. The INR should be recorded if known and if the patient is having their warfarin status monitored. All medication associated with Myocardial events should also be noted.
- Components in order to calculate the SOFA score
- AF resolution

Discharge from Hospital

- Date of hospital discharge
- Mortality status
- All medications should be recorded especially those for risk reduction of stroke (such as anticoagulation with Apixaban or Rivaroxaban or Warfarin or other) and the ongoing treatment with either of the study drugs. The INR should be recorded if known and if the patient is having their warfarin status monitored. All medication associated with Myocardial events should also be noted.
- EQ-5D-5L
- AF resolution

Day 60 (D60) and Day 90 (D90) - Visit can be performed remotely.

- Mortality status
- All medications should be recorded especially those for risk reduction of stroke (such as anticoagulation with Apixaban or Rivaroxaban or Warfarin or other) and the ongoing treatment with either of the study drugs. The INR should be recorded if known and if the patient is having their warfarin status monitored. All medication associated with Myocardial events should also be noted.
- All new contacts with health services including hospital admissions
- New Stroke, TIA, Myocardial or Thromboembolic (PE / DVT) events
- EQ-5D-5L
- Expected Serious Adverse Events:
- Death related to the underlying cause of ICU admission
- Cardiovascular failure, including the need for vasopressors/ inotropes
- Respiratory failure, including mechanical ventilation and acute lung injury
- Hepatic impairment as measured by Bilirubin rise of >100 μ mol/L or Transaminases >1000 IU/L
- Acute Kidney Injury, including the need for renal replacement therapy
- Haematological / coagulation failure, including thrombocytopaenia and Disseminated Intravascular Coagulopathy (DIC)
- Delirium / confusion
- AF resolution

9.1 Schedule of assessments

Table 1 - Schedule of Assessments

Procedure	Baseline (Day 0)	Day 1	Day 2	Day 3	Day7	ICU Discharge	Hospital Discharge	Day 60 (in hospital if necessary) (± 14 days)	Day 90 (± 14 Days)
Eligibility assessment	•								
Consent				•					
Randomisation	•								
Prescription of IMP by clinical team	•								
Demographics (medical records)	•								
Medical history (medical records)	•								
Cardiovascular	•	•	•	•	•				
Biochemistry	•	•	•	•	•				
AF resolution	•	•	•	•	•	•	•		
Expected Serious Adverse Events and Serious Adverse Events		•	•	•	•	•	•	•	•
Mortality and morbidity		•	•	•	•	•	•	•	•
Medications	•	•	•	•	•	•	•	•	•
Quality of life questionnaires (EQ-5D-5L)							•	•	•

10 WITHDRAWAL AND CHANGES IN LEVELS OF PARTICIPATION

Informed consent is defined as the process of learning the key facts about a clinical trial before deciding whether or not to participate. It is a continuous and dynamic process and patients should be asked about their ongoing willingness to continue participation at all visits. Patients should be aware from the beginning that they can freely withdraw (cease to participate) from the trial at any time. A patient may wish to cease to participate in a *particular* aspect of the trial.

Patients found to be ineligible post-randomisation (i.e. they were eligible at the point of randomisation but became ineligible over the course of the trial) should be followed up according to all trial processes and will still have their data analysed unless they explicitly change their level of participation.

The changes in levels of participation within the trial are categorised in the following ways:

No trial intervention: The patient would no longer like to receive the trial intervention but is willing to be followed up in accordance with the schedule of assessments (i.e., the patient has agreed that data can be collected and used in the trial analysis).

No trial related follow-up: The patient does not wish to attend trial visits in accordance with the schedule of assessments but is willing to be followed up at standard clinic visits (i.e., the patient has agreed that data can be collected at standard clinic visits and used in the trial analysis).

No further data collection: The patient is not willing to be followed up in any way for the purposes of the trial AND does not wish for any further data to be collected (i.e., only data collected prior to any changes of levels in participation can be used in the trial analysis).

The details of changes of levels in participation within trial (date, reason and category of status change) should be clearly documented in the source documents.

The Legal Representative and/or Researcher are also able to withdraw the patient for the above reasons.

11 ADVERSE EVENT REPORTING

11.1 Definitions

Table 2 – Adverse event reporting definitions

Severity Definitions	Mild	Awareness of signs or symptoms that do not interferent with the patient's usual activity or are transient a	
		resolved without treatment and with no sequelae.	
	Moderate	A sign or symptom, which interferes with the patient's usual activity.	
	Severe	Incapacity with inability to do work or perform usual activities.	
Adverse Event	AE	Any untoward medical occurrence in a patient administered a medicinal product and which does not necessarily have a causal relationship with this intervention.	
		An AE can therefore be any unfavourable and unintended sign (including abnormal laboratory findings), symptom or disease temporally associated with the use of an investigational medicinal product, whether or not related to the investigational medicinal product.	
Adverse Reaction	AR	All untoward and unintended responses to an IMP related to any dose administered.	
		An AE judged by either the reporting Investigator or Sponsor as having causal relationship to the IMP qualifies as an AR. The expression reasonable causal relationship means to convey in general that there is evidence or argument to suggest a causal relationship.	
Serious Adverse Event	SAE	Any untoward medical occurrence or effect that:	
		Results in death	
		Is life-threatening*	
		Requires hospitalisation or prolongation of existing hospitalisation	
		Results in persistent or significant disability or incapacity	
		Is a congenital anomaly/birth defect	
		Or is otherwise considered medically significant by the Investigator**	
Serious Adverse Reaction	SAR	An AR which also meets the definition of a SAE.	

Unexpected Adverse Reaction UAR An AR, the nature or severity of which is not consistent with the applicable product information (e.g., Investigator Brochure for an unapproved IMP or (compendium of) Summary of Product Characteristics (SPC) for a licensed product). When the outcome of an AR is not consistent with the applicable product information the AR should be considered unexpected. Suspected Unexpected Serious SUSAR A SAR that is unexpected i.e., the nature, or severity of Adverse Reaction the event is not consistent with the applicable product information. A SUSAR should meet the definition of an AR, UAR and SAR.

11.2 Adverse event recording – general

The recording and reporting of adverse events (AEs) will be in accordance with the Principles of Good Clinical Practice (GCP) as set out in the Medicines for Human Use (Clinical Trials) Regulations 2004 and amendments thereof and the requirements of the Health Research Authority (HRA). Definitions for adverse event reporting are listed in **Table 2 – Adverse event reporting definitions** in Section 0.

It is routine practice to record AEs in the patient's medical notes and it is also recommended that this includes the documentation of the assessment of severity and seriousness and also of causality (relatedness) in relation to the intervention(s) in accordance with the protocol.

11.3 Adverse event reporting in ABBRUPT

The patients randomised into the ABBRUPT trial are likely to have significant co-morbidities and therefore the frequency of AEs is expected to be high. Most of the AEs occurring in ABBRUPT, whether serious or not, will therefore be anticipated in the sense that they are recognised and accepted complications/consequences of critical illness.

Sites therefore will only report AEs that meet the definition of 'serious', details of which are outlined in Section 11.4.

The reporting period for AEs in the ABBRUPT trial will be from the day of randomisation for 90 days.

11.4 Serious Adverse Advents (SAE) reporting in ABBRUPT

For all SAEs, the PI or delegate must do one of the following:

 Record safety reporting-exempt SAEs in the medical notes but not report them to the ABBRUPT Trials Office as per Section 11.5 11.5 Serious Adverse Events not requiring reporting to the ABBRUPT Trial Office.

^{*} The term life-threatening is defined as diseases or conditions where the likelihood of death is high unless the course of the disease is interrupted.

^{**} Medical events that may not be immediately life-threatening or result in death or hospitalisation but may jeopardise the patient or may require intervention to prevent one of the other outcomes listed in the definitions above.

Report SAEs to the ABBRUPT Trial Office in a non-expedited manner. This can only be done
for the pre-defined subset of SAEs as per Section 11.6 11.6 Serious Adverse Events requiring
non-expedited reporting to the ABBRUPT Trial Office.

Report SAEs to the ABBRUPT Trial Office in an expedited manner (within 24 hours of the site
research team becoming aware of the event). All SAEs not covered by the above 2 categories
must be reported as per Section 11.7 11.8 SAE Reporting process.

Note: when a SAE occurs at the same hospital at which the patient is receiving trial intervention or is being followed up for trial purposes, processes must be in place to make the trial team at the hospital aware of any SAEs, regardless of which department first becomes aware of the event, in an expedited manner.

11.5 Serious Adverse Events not requiring reporting to the ABBRUPT Trial Office

Participation in the trial will be for 90 days following randomisation. At whatever time they occur during the patient's participation, from the time the intervention started to the end of patient follow-up, the following are not considered to be critical to the evaluation of the safety of the trial:

- Known complications of the underlying cause of the patient's ICU admission (not including death; please refer to section 11.6).
- Pre-planned hospitalisation(s) following patient discharge

All events which meet the definition of serious must be recorded in the patient's notes, including the causality and severity, throughout the patient's time on trial, including follow-up, but for trial purposes these events do not require reporting on the SAE Form. Such events are 'safety reporting exempt'.

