11.6 Serious Adverse Events requiring non-expedited reporting to the ABBRUPT Trial Office

Where the safety profile is well established, the causal relationship between the intervention (or the patient's underlying condition), and the SAE, may be known. That is, such events are protocol-defined as 'expected' (see Section 11.10 11.11 Assessment of expectedness of an SAE by the CI).

Such events should still be recorded by the trial team in the patient's notes and reported to the ABBRUPT Trial Office on the appropriate follow-up CRF but it does not require expedited reporting (immediately on the site becoming aware of the event) since the assessment of expectedness for the specified events has been pre-defined. These include:

- Death related to the underlying cause of ICU admission
- Cardiovascular failure, including the need for vasopressors/ inotropes
- Respiratory failure, including mechanical ventilation and acute lung injury
- Hepatic impairment as measured by Bilirubin rise of >100 μ mol/L or Transaminases >1000 μ L/L
- Acute Kidney Injury, including the need for renal replacement therapy
- Haematological / coagulation failure, including thrombocytopaenia and Disseminated Intravascular Coagulopathy (DIC)
- Delirium
- Sepsis (as defined by The Third International Consensus Definitions for Sepsis and Septic Shock)

ABBRUPT: Protocol

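### Organ failures, delirium and sepsis that complicate the admission illness meet both the do-not-report rule (11.5) and the CRF-reporting rule (11.6), and sepsis is missing from the Section 9 lists

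*Protocol*

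**What the plan says.** Section 11.4 sets the frame: "For all SAEs, the PI or delegate must do one of the following". Three routes follow.

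- **Exempt.** "Record safety reporting-exempt SAEs in the medical notes but not report them to the ABBRUPT Trials Office". Section 11.5 defines this class. Apart from planned admissions after discharge, it holds one open category, which applies throughout follow-up: "Known complications of the underlying cause of the patient's ICU admission (not including death; please refer to section 11.6". The section closes by saying that "for trial purposes these events do not require reporting on the SAE Form. Such events are 'safety reporting exempt".
- **Non-expedited.** Section 11.6 lists events that are to be "reported to the ABBRUPT Trial Office on the appropriate follow-up CRF but it does not require expedited reporting". Its stated ground is that "the causal relationship between the intervention (or the patient's underlying condition), and the SAE, may be known". The list covers death from the admission cause, five organ-system items, delirium and "Sepsis (as defined by The Third International Consensus Definitions for Sepsis and Septic Shock".
- **Expedited.** Section 11.7 sends everything outside 11.5 and 11.6 to the SAE Form within 24 hours.

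Section 9 sets out the expected SAEs to be collected in two places, one for Days 1, 2, 3 and 7 and one for Days 60 and 90. Table 1 has a general row for expected and other SAEs at every visit after baseline. Section 6.6 states that the trial is open label.

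**The concern.** The two classes rest on overlapping ground. Section 11.5 exempts complications of the illness that brought the patient to ICU. Section 11.6 counts the patient's underlying condition among the causes that make an event expected and CRF-reportable. Take vasopressor-requiring cardiovascular failure in a patient admitted with septic shock. Under 11.5 it can stay in the notes, and under 11.6 it must go on the follow-up CRF. Two sites can do opposite things and both comply.

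What is at stake is the completeness of the SAE data that the DMC may review (Section 11.12) and that the final report would tabulate. Independent causality review by the CI starts on receipt of an SAE Form (Section 11.10). Neither the exempt nor the non-expedited route uses that form, so for these events the follow-up CRF is the only systematic route to the Trial Office. The person choosing the route knows the allocation.

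Sepsis raises a separate problem. Its place in 11.6 removes it from the SAE Form, yet the visit lists that a CRF designer would work from do not mention it.

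**Working it through.** No figure in the protocol is in question, so the check compares the lists item by item.

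| Expected SAE in 11.6 | Carved out of the 11.5 exemption? | In the Section 9 D1–D7 list? | In the Section 9 D60/D90 list? |
|---|---|---|---|
| Death from the admission cause | Yes | Yes | Yes |
| Cardiovascular failure | No | Yes | Yes |
| Respiratory failure | No | Yes | Yes |
| Hepatic impairment | No | Yes | Yes |
| Acute kidney injury | No | Yes | Yes |
| Haematological/coagulation failure | No | Yes | Yes |
| Delirium | No | Yes (with confusion) | Yes (with confusion) |
| Sepsis | No | No | No |

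**Overlap.** Of 8 items, 1 is carved out, which leaves 8 − 1 = 7 that can meet both rules. The carve-out for death points the reader to 11.6. The overlap was therefore recognised for one item and left open for the rest.

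**Section 9.** Each list holds 7 of the 8 items, and the missing one is sepsis both times. The amendment table records that sepsis was added as an expected SAE in version 2.0, so its place in 11.6 is deliberate.

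**Route for sepsis.** Because 11.6 lists it, 11.7 does not send it to the SAE Form. That leaves the follow-up CRF. Section 9 does not ask for it there by name; the general SAE row of Table 1 may cover it.

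**Effect on a comparison between arms.** Let p be the true risk of a listed event in an arm and r the fraction of such events sent to the Trial Office. The reported risk is then p × r, and the reported risk ratio is

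(p_A × r_A) / (p_B × r_B) = (p_A / p_B) × (r_A / r_B).

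- If r_A = r_B = r, the ratio is unchanged. Counts fall, and the absolute difference shrinks to r × (p_A − p_B).
- If r_A and r_B differ, the ratio is multiplied by r_A / r_B.

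Hospital is a minimisation variable (Section 6.5). Reporting habits that differ between sites but treat both arms alike therefore mostly fall in the first case. The second needs the routing decision to depend on the arm within a site. The protocol gives neither p nor r, so no size can be calculated from it.

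**The case against.** The best case for the current text has three parts.

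- **A compatible reading exists.** The last sentences of 11.5 waive only the SAE Form, and 11.6 events do not use that form. The specific 11.6 list could also be taken to override the general wording of 11.5. But the heading of 11.5 and the first route in 11.4 both say that exempt events do not go to the Trial Office at all, and nothing states that the specific list prevails. The compatible reading is available to a site but not required of it.
- **Section 9 and Table 1 already ask for most of these events.** Seven of the eight items are named at Days 1, 2, 3, 7, 60 and 90, with no condition on cause except for death. This stands and makes large-scale omission less likely. It does not remove the conflicting instruction in 11.4 and 11.5.
- **Sepsis may still be captured.** Section 11.6 itself sends it to the follow-up CRF, Table 6 says that those CRFs carry non-expedited SAEs, and Table 1 has its general row. The Section 9 lists are also not a full CRF specification, since they show no SAE items at ICU or hospital discharge where Table 1 requires them. This stands too: the gap makes capture uncertain and does not show that sepsis is lost.

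A reader might infer more than the text supports. Section 11.5 names no organ failure, so the overlap covers listed events that are known complications of the admission cause, not every organ failure. Section 11.3 does not fill that gap. It calls most adverse events "anticipated in the sense that they are recognised and accepted complications/consequences of critical illness", but names no organ failure and does not refer to the cause of admission. Nor do the documents show that routing will differ by arm.

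**Conclusion.** The point holds as a contradiction between reporting rules together with a list mismatch. Seven of the eight expected SAEs in 11.6 can meet both the exempt and the CRF-reporting definitions when they complicate the admission illness, only one route is allowed, and no order of precedence is given. Sepsis is absent from both Section 9 lists. The sepsis gap is separate and is not a cause of the site judgement.

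The consequence is SAE counts that may be incomplete and depend on how each site reads 11.5. Because the trial is open label, a reader might conclude that the SAE comparison between arms will be biased. That is only a risk: it needs arm-dependent routing, which nothing in the documents demonstrates.

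The reach is limited. The primary outcome is death from any cause and does not pass through this routing. The Section 8.2 safety outcomes, including hypotension requiring intervention, bradycardia and heart block, are defined separately. Vasopressor and inotrope use is also recorded in its own right at Days 0 to 3 and 7. The point is worth correcting because it affects the safety record and costs little to correct; it does not threaten the main result.

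**What to change.** 1. In Section 11.5, add a sentence such as: *Events listed in Section 11.6 are always reported on the follow-up CRF, whatever their cause; this exemption applies only to other complications.*
2. Add sepsis, with the 11.6 definition, to both Section 9 expected-SAE lists (Days 1–7 and Days 60/90) and to the matching CRFs.

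The cost is a line or two of protocol text, a CRF item and a note to sites. The downside is a few more CRF entries, all non-expedited. Clinical management does not change. If patients have already been recruited, the report should state from which date the clarified rule applied, because counts before and after it may not be comparable.
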